16.4.4. Durability of Response

Durability overall response will be estimated using the Kaplan-Meier method. Approximate 95% confidence intervals for median duration of response will be computed using the formula proposed by Brookmeyer and Crowley. The same method will be applied to hepatosplenic response and anemia response for Arms A, B, E, F, and D and erythroid response for Arm G.

16.5. Exploratory Outcomes (to Be Evaluated in Each Arm Independently)

Due to the small overall sample size, the results of the following analyses will be considered exploratory and hypothesis-generating in nature.

16.5.1. Bone Marrow Histology and JAK2V617F Allele Burden

Bone marrow fibrosis and granulocyte JAK2V617F allele burden will be assessed for all patients at baseline and at the time of the response bone marrow examination for patients who achieve a CR, PR, or CI for Arms A, B, C, E, and F, CR, PR, and HI for Arm G and for patients achieving durable (2 months or more) decrease in peripheral blood and bone marrow blast to less than 5% for Arm D. Bone marrow fibrosis grade will be evaluated by a central review pathologist and the fibrosis grade will be confirmed by the PI. The proportion of patients achieving reversal of bone marrow fibrosis to a lower grade will be assessed and reported descriptively. JAK2V617F allele burden will be summarized descriptively at each time point and changes over time will be evaluated.

16.5.2. Leukocytosis, Thrombocytosis, Peripheral Blood Blast and Immature Cell Count

The proportion of patients with baseline leukocytosis, thrombocytosis or increased peripheral blood blast or immature cell count, who achieve normalization or at least a 50% reduction in their counts will be calculated and reported descriptively

16.6. Over Accrual

If more than the target number of patients are accrued, the additional patients will be included in final endpoint estimates and confidence intervals.

16.7. Data and Safety Monitoring

A safety committee internal to Janssen Research & Development will review the safety data after approximately every 3 months until all patients have terminated from the study. The safety review committee will consist of a study responsible physician, safety physician and a

biostatistician. The findings of the safety committee will be shared with the study Investigator. The study responsible physician or safety physician may convene a meeting sooner should any concerns arise from review of data or from the Investigator.

In addition to the safety committee, an independent hepatic safety panel will review emergent relevant safety data, if needed. If there is evidence that imetelstat is responsible for the occurrence of a life-threatening, irreversible, or fatal hepatotoxicity a full investigation will be conducted on the data available for imetelstat treatment of patients with myelofibrosis. The investigation may include, but is not limited to, a benefit-risk analysis with external adjudication by the hepatic safety panel and other specialties as necessary. Trial modifications, including trial closure, will be considered based on the results of this investigation.

16.8. Adverse Event Stopping Rules (to Be Evaluated in Each Arm Independently)

The stopping rules specified below are based on the knowledge available at study development. We note that the Adverse Event Stopping Rule may be adjusted in the event of either (1) the study re-opening to accrual or (2) at any time during the conduct of the trial and in consideration of newly acquired information regarding the adverse event profile of the treatment(s) under investigation. The study team may choose to suspend accrual because of unexpected adverse event profiles that have not crossed the specified rule below.

Accrual will be temporarily suspended to this study if at any time we observe events considered at least possibly related to study treatment (i.e. an adverse event with attribute specified as “possible”, “probable”, or “definite”) that satisfy either of the following:

- If 3 or more out of the first 10 treated patients experience Grade 4 non-hematological toxicities
- If after the first 10 patients have been treated, 30% of patients experience Grade 4 non-hematologic toxicities

We note that we will review Grade 4 and 5 adverse events deemed “unrelated” or “unlikely to be related”, to verify their attribution and to monitor the emergence of a previously unrecognized treatment-related adverse event.

At study activation, this study will have been registered within the “ClinicalTrials.gov” web site. The Primary and Secondary Endpoints (i.e., “Outcome Measures”) along with other required information for this study will be reported on ClinicalTrials.gov.

16.9. Inclusion of Women and Minorities

This study will be available to all eligible patients, regardless of race, gender, or ethnic origin.

There is no information currently available regarding differential effects of this regimen in subsets defined by race, gender, or ethnicity, and there is no reason to expect such differences to

exist. Therefore, although the planned analysis will, as always, look for differences in treatment effect based on racial and gender groupings, the sample size is not increased in order to provide additional power for subset analyses.

The geographical region served by MCCC has a population which includes approximately 3% minorities. Based on prior MCCC studies involving similar disease sites, we expect about 3% of patients will be classified as minorities by race and about 50% of patients will be women. Expected sizes of racial by gender subsets are shown in [Table 18](#) below.

Table 18: Expected Sizes of Racial by Gender Subsets

Ethnic Category	Sex/Gender			
	Females	Males	Unknown	Total
Hispanic or Latino	1	1	0	2
Not Hispanic or Latino	73	73	0	146
Unknown	0	0	0	0
Ethnic Category: Total of all subjects	74	74	0	148
Racial Category				
American Indian or Alaskan Native	0	0	0	0
Asian	0	0	0	0
Black or African American	2	2	0	4
Native Hawaiian or other Pacific Islander	0	0	0	0
White	72	72	0	144
More than one race	0	0	0	0
Unknown	0	0	0	0
Racial Category: Total of all subjects	74	74	0	148

Ethnic Categories: **Hispanic or Latino** – a person of Cuban, Mexican, Puerto Rico, South or Central American, or other Spanish culture or origin, regardless of race. The term “Spanish origin” can also be used in addition to “Hispanic or Latino.”

Not Hispanic or Latino

Racial Categories: **American Indian or Alaskan Native** – a person having origins in any of the original peoples of North, Central, or South America, and who maintains tribal affiliations or community attachment.

Asian – a person having origins in any of the original peoples of the Far East, Southeast Asia, or the Indian subcontinent including, for example, Cambodia, China, India, Japan, Korea, Malaysia, Pakistan, the Philippine Islands, Thailand, and Vietnam. (Note: Individuals from the Philippine Islands have been recorded as Pacific Islanders in previous data collection strategies.)

Black or African American – a person having origins in any of the black racial groups of Africa. Terms such as “Haitian” or “Negro” can be used in addition to “Black or African American.”

Native Hawaiian or other Pacific Islander – a person having origins in any of the original peoples of Hawaii, Guam, Samoa, or other Pacific Islands.

White – a person having origins in any of the original peoples of Europe, the Middle East, or North Africa.

17. PATHOLOGY CONSIDERATIONS/TISSUE BIOSPECIMENS

Central review of the bone marrow will be performed by Dr. [REDACTED] at the Mayo Clinic in Rochester, MN. Fibrosis grading and other histology changes will be documented.

17.1. Tissue and Biospecimen Submission

Table 19: Summary Table of Tissue Biospecimens for this Protocol

Type of Tissue Biospecimen to Submit	Mandatory or Optional	When to Submit	Reason for Submission
Initial Bone Marrow Biopsies	Mandatory	
Patients who achieve a CR, PR, or CI in the core phase (Cycles 1-9)¹: Submit with the response bone marrow biopsy
 
Patients who do not achieve a CR, PR, or CI in the core phase (Cycles 1-9): Submit at the end of Cycle 9 or at the time of early discontinuation if patient receives < 9 cycles
	Central review to evaluate extent of marrow involvement by myelofibrosis, bone marrow cellularity and percentage of blasts and ring sideroblasts
Response Bone Marrow Biopsies in patients who achieve a CR, PR, or CI during the core phase	Mandatory	≤30 days after response bone marrow biopsy	Central review to evaluate extent of marrow involvement by myelofibrosis, bone marrow cellularity and percentage of blasts and ring sideroblasts

¹ During the core phase 9 cycles, PR, or CI by the end of Cycle 9: Submit at the end of Cycle 9 or at the time of early discontinuation.

17.2. Initial and Response Evaluation Materials

Submit the following materials to Dr. [REDACTED]:

- 8-10 unstained and charged slides (or tissue block) from each bone marrow biopsy
- Bone Marrow Form for each bone marrow being submitted
- Baseline and Response Bone Marrow Biopsy Report

Slides should be placed in appropriate slide container(s) and labeled with the protocol number, study patient number, and patient initials.

The pathologist will forward the completed Bone Marrow Form and accompanying reports to the study QAS for scanning and data entry purposes to the following:

QAS for CP14B019 (formerly MC1285)

[name]

[name]

[name]

Phone: [REDACTED]

Refer to Test Schedule (Section 4). Data will be collected using an electronic data capture system (EDC) based upon pre-specified electronic case report forms (eCRFs) and completion guidelines (CCGs).

APPENDIX A. DIPSS-PLUS RISK CATEGORIES IN MYELOFIBROSIS.

The Dynamic International Prognostic Scoring System (DIPSS)-plus prognostic model for primary myelofibrosis (PMF). The DIPSS-plus prognostic model for PMF uses 8 risk factors to predict survival: age >65 years, hemoglobin level <10 g/dL, leukocyte count >25 × 10⁹/L, circulating blasts ≥ 1%, presence of constitutional symptoms, presence of unfavorable karyotype, platelet count <100 × 10⁹/L, and the presence of red cell transfusion need.

* Transfusion dependency is defined by a history of at least 2 units of red blood cell transfusions in the last month for a hemoglobin level of less than 85 g/L that was not associated with clinically overt bleeding. Please note that a transfusion-dependent patient automatically has 2 risk factors because of transfusion need (1 risk point) and hemoglobin level <10 g/dL (1 risk point).

** Constitutional symptoms constitute weight loss >10% of baseline value in the year preceding diagnosis, unexplained fever, or excessive sweats persisting for >1 month.

*** Unfavorable karyotype constitutes complex karyotype or sole or 2 abnormalities that include +8, -7/7q-, i(17q), inv(3), -5/5q- 12p-, or 11q23 rearrangement.

**APPENDIX B. WORLD HEALTH ORGANIZATION (WHO)
DIAGNOSTIC CRITERIA FOR POLYCYTHEMIA VERA,
ESSENTIAL THROMBOCYTHEMIA AND PRIMARY
MYELOFIBROSIS³**

2008 WHO Diagnostic Criteria					
		Polycythemia Vera ¹	Essential Thrombocythemia ¹		Primary Myelofibrosis ¹
Major criteria	¹	Hgb > 18.5 g/dL (men) > 16.5 g/dL (women) Or ²	1 Platelet count $\geq 450 \times 10^9/L$	1	Megakaryocyte proliferation and atypia*** ³ accompanied by either reticulin and/or collagen fibrosis, or ⁴
	²	Presence of JAK2V617F or JAK2 exon 12 mutation	2 Megakaryocyte proliferation with large and mature morphology. 3 Not meeting WHO criteria for CML, PV, PMF, MDS or other myeloid neoplasm 4 Demonstration of JAK2V617F or other clonal marker or no evidence of reactive thrombocytosis	2 3 4	Not meeting WHO criteria for CML, PV, MDS, or other myeloid neoplasm Demonstration of JAK2V617F or other clonal marker or no evidence of reactive marrow fibrosis
Minor criteria	¹	BM trilineage myeloproliferation		1	Leukoerythroblastosis
	²	Subnormal serum Epo level		2	Increased serum LDH level
	³	EEC growth		3	Anemia
				4	Palpable splenomegaly

Key: BM, bone marrow; Hgb, hemoglobin; Hct, hematocrit; Epo, erythropoietin; EEC, endogenous erythroid colony; WHO, World Health Organization; CML, chronic myelogenous leukemia; PV, polycythemia vera; PMF, primary myelofibrosis; MDS, myelodysplastic syndromes; LDH, lactate dehydrogenase

¹ PV diagnosis requires meeting either both major criteria and one minor criterion **or** the first major criterion and 2 minor criteria. ET diagnosis requires meeting all 4 major criteria. PMF diagnosis requires meeting all 3 major criteria and two minor criteria.

² **Or** Hgb or Hct $> 99^{\text{th}}$ percentile of reference range for age, sex, or altitude of residence **or** red cell mass $> 25\%$ above mean normal predicted **or** Hgb $> 17 \text{ g/dL (men)}/> 15 \text{ g/dL (women)}$ if associated with a sustained increase of $\geq 2 \text{ g/dL}$ from baseline that cannot be attributed to correction of iron deficiency

³ Small to large megakaryocytes with aberrant nuclear/cytoplasmic ratio and hyperchromatic and irregularly folded nuclei and dense clustering.

⁴ In the absence of reticulin fibrosis, the megakaryocyte changes must be accompanied by increased marrow cellularity, granulocytic proliferation and often decreased erythropoiesis (i.e. pre-fibrotic PMF).

**APPENDIX C. INTERNATIONAL WORKING GROUP FOR
MYELOPROLIFERATIVE NEOPLASMS RESEARCH
AND TREATMENT (IWG-MRT) RECOMMENDED
CRITERIA FOR POST-POLYCYTHEMIA VERA AND
POST-ESSENTIAL THROMBOCYTHEMIA
MYELOFIBROSIS**

Criteria for post-polycythemia vera myelofibrosis	
Required criteria:	
1	Documentation of a previous diagnosis of polycythemia vera as defined by the WHO criteria
2	Bone marrow fibrosis Grade 2–3 (on 0–3 scale) or Grade 3–4 (on 0–4 scale) (see footnote for details)
Additional criteria (two are required):	
1	Anemia or sustained loss of requirement for phlebotomy in the absence of cytoreductive therapy
2	A leukoerythroblastic peripheral blood picture
3	Increasing splenomegaly defined as either an increase in palpable splenomegaly of ≥ 5 cm (distance of the tip of the spleen from the left costal margin) or the appearance of a newly palpable splenomegaly
4	Development of ≥ 1 of three constitutional symptoms: $>10\%$ weight loss in 6 months, night sweats, unexplained fever ($>37.5^{\circ}\text{C}$)
Criteria for post-essential thrombocythemia myelofibrosis	
Required criteria:	
1	Documentation of a previous diagnosis of essential thrombocythemia as defined by the WHO
2	Bone marrow fibrosis Grade 2–3 (on 0–3 scale) or Grade 3–4 (on 0–4 scale) (see footnote for details)
Additional criteria (two are required):	
1	Anemia and a ≥ 2 g/dL decrease from baseline hemoglobin level
2	A leukoerythroblastic peripheral blood picture
3	Increasing splenomegaly defined as either an increase in palpable splenomegaly of ≥ 5 cm (distance of the tip of the spleen from the left costal margin) or the appearance of a newly palpable splenomegaly
4	Increased lactate dehydrogenase
5	Development of ≥ 1 of three constitutional symptoms: $>10\%$ weight loss in 6 months, night sweats, unexplained fever ($>37.5^{\circ}\text{C}$)

Note: Grade 2–3 according to the European classification:⁵ diffuse, often coarse fiber network with no evidence of collagenization (negative trichrome stain) or diffuse, coarse fiber network with areas of collagenization (positive trichrome stain). Grade 3–4 according to the standard classification:⁶ diffuse and dense increase in reticulin with extensive intersections, occasionally with only focal bundles of collagen and/or focal osteosclerosis or diffuse and dense increase in reticulin with extensive intersections with coarse bundles of collagen, often associated with significant osteosclerosis.

APPENDIX D. PERFORMANCE STATUS SCALE

Grade	Description
0	Fully active, able to carry on all pre-disease performance without restriction
1	Restricted in physically strenuous activity but ambulatory and able to carry out work of a light or sedentary nature, e.g., light housework or office work
2	Ambulatory and capable of all self-care but unable to carry out any work activities. Up and about > 50% of waking hours
3	Capable of only limited self-care, confined to a bed or chair > 50% of waking hours
4	Completely disabled. Cannot carry on any self-care. Totally confined to bed or chair
5	Dead

AMENDMENT HISTORY

Draft: June 30, 2017

ABBREVIATIONS

AE	Adverse Event
CI	Clinical Improvement
CR	Complete Remission
DIPSS	Dynamic International Prognostic Scoring System
DoR	Duration of Response
ECOG	Eastern Cooperative Oncology Group
eCRF	Electronic Case Report Form
ET MF	Essential Thrombocythemia Myelofibrosis
HI	Hematological Improvement
IV	Intravenous
IWG-MRT	International Working Group for Myeloproliferative Neoplasms Research and Treatment
MDS	Myelodysplastic Syndromes
MedDRA	Medical Dictionary for Regulatory Activities
MF	Myelofibrosis
MPN	Myeloproliferative Neoplasm
NCI CTCAE	National Cancer Institute Common Terminology Criteria for Adverse Events
OS	Overall Survival
PMF	Primary Myelofibrosis
PR	Partial Remission
PV	Polycythemia Vera
SAP	Statistical Analysis Plan
SD	Standard Deviation
SMQs	Standardized MedDRA Queries
WBC	White Blood Cell

1. INTRODUCTION

This statistical analysis plan (SAP) is to lay out key analysis elements including definitions of analysis sets, derived variables, and statistical methods for the planned analyses for imetelstat (JNJ-63935937) Study CP14B019.

1.1. Trial Objectives

Primary Objective

To evaluate overall response rate in each of the six study arms (Arm A, B, D, E, F and G). The overall response rate for Arm C will be grouped with either A or B for analysis.

Response for Arms A, B, E, and F will be evaluated according to IWG-MRT criteria. For arm G, response will be according to the International Working Group response assessment as reported by Cheson et al. (2006). Response for Arm D will be defined by reduction in peripheral blood and bone marrow blast count to <5% and lasting for at least 2 months.

Secondary Objectives

- To evaluate the safety and tolerability of imetelstat in each arm (per NCI CTCAE, v4.0).
- To evaluate the efficacy of imetelstat in the reduction of spleen size, as measured by physical examination (palpable distance from the left costal margin) in each arm.
- To evaluate the efficacy of imetelstat in improving anemia or inducing red blood cell transfusion-independence in previously transfusion-dependent subjects (per IWG-MRT criteria) in each arm.
- To evaluate onset and durability of response as defined in primary and secondary endpoints in each arm.

Exploratory Objectives

[figure not shown]
- To evaluate the effect of imetelstat on bone marrow histology, karyotype, and JAK2V617F allele burden in each arm.
- To evaluate the effect of imetelstat on leukocytosis, circulating blast count (blast % x WBC), circulating immature myeloid cell count (sum of blast, promyelocyte, myelocyte, and metamyelocyte % x WBC), and thrombocytosis in each arm.

1.2. Trial Design

[figure not shown]
This was a single center, open-label study of imetelstat in subjects with Intermediate-2 or high risk PMF/post-ET/PV MF (Arms A, B, C, E and F) or blast-phase MF (Arm D only) or spliceosome-mutated (or with ring sideroblasts) MDS/MPN (Arm G only).

As of 22 January 2014, all arms were permanently closed to accrual.

[figure not shown]
1.2.1. Arm A Treatment Schedule

1.2.2. Arm B Treatment Schedule

[figure not shown]

1.2.3. Arm C and D Treatment Schedule

[figure not shown]
1.2.4. Arm E Treatment Schedule

(myelofibrosis subjects with spliceosome mutations or ring sideroblasts)

[figure not shown]
1.2.5. Arm F Treatment Schedule

(myelofibrosis subjects without spliceosome mutations or ring sideroblasts)

1.2.6. Arm G Treatment Schedule

(MDS/MPN or MDS subjects with spliceosome mutations or ring sideroblasts)

1.3. Sample Size Justification

As a pilot study, the trial was not designed as a fixed sample size study. Instead, the probability of success or futility was estimated under the assumption of various response rates, and the number of subjects was adjusted based on the independent evaluation of each study arm during the trial.

As of protocol Addendum 3, accrual to Arm C was permanently discontinued. The 11 subjects slotted to enroll on Arm C were treated per the Arm A or Arm B dose schedule. A total of 34 subjects were to be accrued between Arms A, B, and C. Accrual was to continue per protocol in Arm D and three additional arms (Arms E, F, and G) were added. A total of 26 evaluable subjects (Arms D and G) or 25 evaluable subjects (Arms E and F) were to be accrued in each of the remaining arms. An additional 3 subjects were to be accrued in each arm to account for subjects who needed to be replaced. Therefore, the maximum overall sample size across all arms of the study was 148 subjects.

As of 22 January 2014, the study was closed to enrollment with a total of 80 subjects enrolled.

2. GENERAL ANALYSIS DEFINITIONS

In general, continuous variables will be summarized using descriptive statistics such as mean, standard deviation (SD), median, and range. Categorical variables will be summarized using frequency and percentage. For time-to-event variables, the Kaplan-Meier method will be used for descriptive summaries and for each study arm independently unless otherwise specified.

2.1. Baseline

Unless specified otherwise, the baseline value for each arm is defined as the last non-missing value collected on or before the administration of the first dose of study drug.

2.2. Study Day

Study Day 1 is defined as the day of the first dose of study drug that a subject received.

Study Day = assessment date – Study Day 1 + 1.

2.3. Missing and Partial Dates

In general, imputation of partial missing dates will be made for AE onset date, AE resolution date, date of death, start and end dates of concomitant therapy, and date of initial diagnosis.

For AE onset and resolution date, imputation rules listed below will be applied.

- Partial AE onset dates will be imputed as follows:
 - If the onset date of an adverse event is missing day only, it will be set to:
 - First day of the month that the AE occurred, if month/year of the onset of AE is different than the month/year of the first dose date
 - The day of first dose date, if the month/year of the onset of AE is the same as month/year of the first dose date and month/year of the AE resolution date is different
 - The day of first dose date or day of AE resolution date, whichever is earliest, if month/year of the onset of AE and month/year of the first dose date and month/year of the AE resolution date are same

- If the onset date of an adverse event is missing both day and month, it will be set to the earliest of:
 - January 1 of the year of onset, as long as this date is after the first dose date
 - Month and day of the first dose date, if this date is the same year that the AE occurred
 - The AE resolution date.
- Completely missing onset dates will not be imputed.
- Partial AE resolution dates not marked as ongoing will be imputed as follows:
 - If the resolution date of an adverse event is missing day only, it will be set to the earliest of the last day of the month of occurrence of resolution or the day of the date of death, if the death occurred in that month.
 - If the resolution date of an adverse event is missing both day and month, it will be set to the earliest of December 31 of the year or the day and month of the date of death, if the death occurred in that year.
 - Completely missing resolution dates will not be imputed.

For start and end dates of concomitant therapies, if the start or end date is completely missing, no imputation will be performed. If the start or end date is partially missing, the following imputation rules will be used.

- If only the day is missing, the 15th day of the month will be used.
- If both the day and month are missing, the 30th of June will be used.

If the medication/therapy was taken prior to study start, and the imputed start date is after first dosing date, further adjust the imputed start date as the day prior to first dosing date; if the medication/therapy was taken after study start, and the imputed start date is prior to first dosing date, further adjust the imputed start date as first dosing date. Also adjust the imputed medication/therapy end date so that it is on or after first dosing date.

For date of death and date of initial diagnosis, the following rule will be applied.

- If date is completely missing, no imputation will be made.
- If year is missing, no imputation will be made.
- If only year is present but month and day are missing, then June 30th will be used.
- If only day is missing but year and month are available, then the 15th of the month will be used.

However, the above imputations will be modified by the following rules:

- If such imputed date for initial diagnosis is on or after study consent date, then consent date - 1 will be used.
- If the imputed date is for a date of death and is before the last date that the subject is known to be alive, the latter date + 1 will be used.

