10.1.1. Adverse Event

An AE is any unfavorable and unintended sign, symptom, or disease temporally associated with the use of an investigational product or other protocol-imposed intervention, regardless of attribution.

During the extended hepatic safety follow-up, once patients have discontinued imetelstat treatment, an AE is defined as an unfavorable and unintended sign, symptom, or disease occurring during the follow-up period or temporally associated with a protocol-imposed intervention, regardless of attribution.

This includes the following:

- AEs not previously observed in the patient that emerge during the protocol-specified AE reporting period, including signs or symptoms associated with MF that were not present prior to the AE reporting period (see Section 10.2.1)
- Complications that occur as a result of protocol-mandated interventions (e.g., invasive procedures such as biopsies)
- AEs that occur prior to assignment of study treatment that are related to a protocol-mandated intervention (e.g., invasive procedures such as biopsies, medication washout, or no treatment run-in)
- Preexisting medical conditions, judged by the Investigator to have worsened in severity or frequency or changed in character during the protocol-specified AE reporting period

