5.1. Adverse Events

The verbatim terms used in the eCRF by investigators to identify AEs will be coded using the Medical Dictionary for Regulatory Activities (MedDRA). The severity of adverse events is assessed in National Cancer Institute (NCI) common terminology criteria for adverse events (CTCAE) Version 4.0.

Treatment-emergent AEs will be defined as those events that 1) occur on or after the first dose of study drug, through the treatment phase, and for 30 days following the last dose of study drug or until subsequent anti-cancer therapy if earlier; 2) any event that is considered study drug-related regardless of the start date of the event; or 3) any event that is present at baseline but worsens in severity or is subsequently considered drug-related by the investigator.

An overview summary table of treatment-emergent AEs will be provided, including drug related AEs, CTCAE grade ≥ 3 AEs, serious AEs, and deaths.

Treatment-emergent AEs will be summarized by system organ class and preferred terms. For each treatment-emergent adverse event, the percentage of subjects who experience at least 1 occurrence of the given event will be summarized. Tables will be sorted by frequency in incidence (the highest to lowest incidence) in the total column. The same summary will be provided for the treatment-emergent AEs with CTCAE grade ≥ 3 , treatment-emergent AEs considered related to study treatment, and serious treatment-emergent AEs.

A summary of the number of subjects who discontinued study treatment because of 1 or more AEs by system organ class and preferred term will be provided. This table includes AEs leading to discontinuation of study treatment for those subjects indicated as having discontinued study treatment due to an adverse event on the end of treatment eCRF page.

Treatment-emergent bleeding events will be identified using standardized MedDRA queries (SMQs) by matching the event terms in SMQ "HAEMORRHAGES" and the first SMQ subcategory "HAEMORRHAGE TERM (EXCL LABORATORY TERMS)." The number of subjects with treatment-emergent bleeding events will be summarized for each treatment arm.

A listing of all adverse events will be provided.

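### For an adverse event whose onset is known only to a year before first dose, SAP 2.3 sets onset to the resolution date, so some pre-treatment events count as treatment-emergent

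*SAP*

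**What the plan says.** SAP 2.3 has separate rules for two kinds of incomplete onset date.

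- **Day and month missing.** "If the onset date of an adverse event is missing both day and month, it will be set to the earliest of" three candidates. The first candidate is "January 1 of the year of onset, as long as this date is after the first dose date". The second is the date of first dose, provided that treatment began in the onset year. The third carries no condition: it is "the AE resolution date".
- **Day only missing.** If the onset month and year differ from those of first dose, onset is "First day of the month that the AE occurred". There is no requirement that this date follow first dose.

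On resolution dates, a year-only date becomes 31 December of that year, or the date of death if that is earlier in the same year. "Completely missing resolution dates will not be imputed".

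SAP 5.1 gives three routes to treatment-emergent status. Criterion 1 depends on the onset date: events that "occur on or after the first dose of study drug, through the treatment phase", and up to 30 days after the last dose, or until subsequent anti-cancer therapy if that comes first. Criterion 2 takes in drug-related events whatever their start date. Criterion 3 takes in events present at baseline that worsen in severity or are later judged drug-related.

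**The concern.** A year-only onset is uncertain within the year, but if that year is before the first-dose year there is no doubt that the event began before treatment. The rule discards that information. Its first two candidates are written for onsets in the year of first dose or later, so a prior-year onset falls through to the resolution date, which is the end of the event. Where that date lies on treatment, a pre-treatment event enters the treatment-emergent tables for its term. If there is no resolution date, the rule gives no onset at all and criterion 1 cannot be evaluated.

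SAP 2.3 guards against this kind of error for other dates. A therapy taken before study start whose imputed start falls after first dose is moved to the day before first dose. An initial diagnosis imputed on or after consent is moved to the day before consent. The year-only adverse event rule has no such guard, which looks like an oversight.

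**Working it through.** The plan states no figure for this rule, so there is none to reproduce. The check applies the rule literally, as the minimum of the candidates that qualify, and then applies criterion 1.

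**Assumed dates (not from the documents):** first dose 15 March 2013, last dose 1 December 2013. Criterion 1 then runs from 15 March 2013 to 1 December + 30 days = 31 December 2013, if no other anti-cancer therapy starts earlier.

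**Onset year 2012, candidate by candidate:**

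1. 1 January 2012 is not after 15 March 2013, so it does not qualify.
2. The first dose date is in 2013, not 2012, so it does not qualify.
3. The resolution date always qualifies when there is one.

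For every possible resolution date from 1 January 2012 to 31 December 2014 (1096 days), the rule returned the resolution date 1096 times.

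| Resolution date | Imputed onset | Criterion 1 | Result | Days |
|---|---|---|---|---|
| Before 15 Mar 2013 (e.g. 10 Feb 2013) | Resolution date | Not met | Class right | 439 |
| 15 Mar to 31 Dec 2013 (e.g. 10 Jun 2013) | Resolution date | Met | Class wrong, unless criterion 2 or 3 applies | 292 |
| After 31 Dec 2013 (e.g. 1 Jun 2014) | Resolution date | Not met | Class right, date wrong | 365 |
| Missing or ongoing | None | Cannot be evaluated | Gap | – |

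439 + 292 + 365 = 1096. These counts follow from the assumed dates and do not estimate how often each case would arise.

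**Year-only resolution.** Onset 2012 and resolution 2013, with no death in 2013, gives a resolution date and hence an onset of 31 December 2013. The true onset was no later than 31 December 2012, so the shift is at least one year. The event is treatment-emergent under criterion 1 only if 31 December 2013 lies inside that subject's window. With a last dose on 1 December 2013 it is on the final day; with an earlier last dose it is outside.

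**Other onset years behave sensibly.** An onset of 2013 goes to first dose, or to the resolution date if that is earlier (resolved 1 February 2013 gives 1 February 2013; resolved 1 June 2013 gives 15 March 2013). An onset of 2014 goes to 1 January 2014.

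**Comparison with the day-only rule.** An onset recorded as November 2012 is set to 1 November 2012 and stays pre-treatment under criterion 1 whatever its resolution date. The same event recorded as 2012, resolving 10 June 2013, is set to 10 June 2013 and meets criterion 1.

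**Size per event.** In an arm of 11 (the stage 1 size in Protocol 16.1), 1/11 = 9.1 points for that term. In a total column of 80, assuming all enrolled subjects were treated, 1/80 = 1.25 points. The documents do not state the number treated in each arm, and under SAP 2.4 the 11 subjects slotted for Arm C are added to Arms A and B.

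**The case against.** The strongest objection is that such records will be rare. Protocol 10.2.1 starts routine adverse event collection after imetelstat is initiated. Screening is at most 14 days before registration (Table 3) and treatment starts at most 7 days after it (Protocol 6.1). A pre-dose event arising under the protocol therefore begins within about 14 + 7 = 21 days of first dose. A prior-year onset then needs a first dose in roughly the first three weeks of January, with the month unrecorded for an event only weeks old. Older conditions are recorded as adverse events only if they worsen (Protocol 10.3.1.6), and worsening in severity is treatment-emergent under criterion 3 anyway. The error can only add a treatment-emergent event and never hide one, and all adverse events are listed regardless.

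This stands as an argument about frequency, but it does not exclude the case. Table 3 records adverse events at screening, Protocol 6.1 requires baseline symptoms to be documented and graded, and Protocol 10.1.1 includes "AEs that occur prior to assignment of study treatment that are related to a protocol-mandated intervention".

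A second objection is that imputing towards treatment-emergent is deliberately conservative. That does not stand. Conservative imputation resolves doubt, and here the recorded year leaves none. Nor is the result consistently conservative, since events resolving after the window fall outside it and ongoing events get no date.

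Stronger readings are tempting but unsupported. A reader might infer that every prior-year onset becomes treatment-emergent; the table shows that only those resolving inside the window do, and only if criteria 2 and 3 do not already apply. A reader might also say that the two onset rules contradict each other. They cover different patterns of missing data and never apply to the same record, so they are inconsistent in outcome but not contradictory.

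**Conclusion.** The defect is real and minor. It follows from the wording of SAP 2.3 and nothing elsewhere in the documents repairs it. Misclassification requires all of the following: onset known to the year only; that year before the year of first dose; resolution between first dose and 30 days after last dose (or subsequent anti-cancer therapy, if earlier); and an event neither drug-related nor worsened from baseline. The undefined onset for ongoing events is a separate gap in the same rule.

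The number of affected records is not given. An assumed range of 0 to 2 seems reasonable, and zero is quite possible. The 9.1 points is what one event would add to a term in an assumed arm of 11, not an estimate of bias in this trial. Only descriptive safety summaries are touched; the response endpoints are not.

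**What to change.** Add one sentence to the year-only rule in SAP 2.3: if the onset year is earlier than the year of first dose, onset is imputed as January 1 of the onset year. In the worked example this gives 1 January 2012 in every case, so criterion 1 is never met, and ongoing events also receive a date. It matches the day-only rule, which takes the start of the known period. Criteria 2 and 3 continue to pick up drug-related and worsened events.

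Imputing 31 December of the onset year, or the resolution date if earlier, gives the same pre-treatment classification. The choice affects only the apparent length of the event, and SAP 5.1 plans no summary of adverse event duration.

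The cost is one sentence and one programming condition. Imputation for onset years equal to or later than the first-dose year is unchanged.
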